## 6.2 EXCLUSION CRITERIA:

Patients will be excluded if at least one of the following criteria is met:

1. Patients on methotrexate or under biologics.
2. Any contraindications regarding the use of azathioprine;
3. Patients who are being treated with any investigational agent;
4. Patients who are not willing to comply with routine clinical appointments.

## 6.3 DISCONTINUATION FROM OBSERVATION PERIOD

In this study, patients will be followed up to a maximum period of 96 weeks. However, observation may be stopped prior to the 96 weeks for different reasons including, but not limited to:

- Patient discontinues the exposure of interest (azathioprine). The introduction of new treatments to CD during the follow up period will not lead to study discontinuation as long as treatment with azathioprine is not discontinued.
- Protocol violation
- Lost to follow up
- Patient withdrawal of consent
- Pregnancy
- Death

In the case observation period is stopped prior to the 96 weeks, the date of study discontinuation, the date of last intake of azathioprine and dose, and the reason for discontinuation should be recorded in the electronic CRF.

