## 9 ENDPOINTS

### 9.1 PRIMARY ENDPOINT

- Proportion of patients who achieve fecal calprotectin remission (< 200 ug/g) at week 12.
- Proportion of patients who maintain fecal calprotectin remission (< 200 ug/g) at week 48 and 96.
- Proportion of patients who maintain fecal calprotectin remission (< 200 ug/g) at each data collection time point up to week 96.

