### 9.2 SECONDARY ENDPOINTS

- **Fecal calprotectin** levels assessed at each data collection time point.
- **Fecal calprotectin** levels and **clinical activity (PCDAI)** at each data collection time point.
- **Fecal calprotectin** levels and **endoscopic activity (Simple endoscopic score for Crohn's disease [SES-CD])** at week 96.
- Proportion of patients with **clinical remission** (PCDAI<10) at each data collection time up to week 96.
- Proportion of patients who achieve **endoscopic remission** (SES-CD ≤ 2) at week 96.
- Proportion of patients on treatment with **azathioprine** at each data collection time point up to week 96.

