## **10.2 SAMPLE SIZE**

It is expected to analyze a total of 80 new patients. This sample size will allow the evaluation of the potential of fecal calprotectin in predicting the induction and maintenance of clinical and endoscopic remission in this population. Regarding the correlation analysis, with this sample size there is a power probability greater than 95% that the lower limit of a one-sided 95% confidence interval is higher than 0.50, if the observed correlation coefficient is at least 0.75.

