**APPENDIX – CHRONOGRAM**

Information to be collected	Data collection time points (96-week follow up)									
	Day 1	W8	W12	W24	W36	W48	W60	W72	W84	W96 or discont. 
Date of birth	X									
Sex	X									
Height	X	X	X	X	X	X	X	X	X	X
Weight	X	X	X	X	X	X	X	X	X	X
BMI	X	X	X	X	X	X	X	X	X	X
Smoking status	X									
Medical history	X									
Comorbidities	X	X	X	X	X	X	X	X	X	X
CD presentation	X									
Diagnosis of CD - location, prognostic classification, extra-abdominal manifestations, anal lesion)	X									
Clinical activity (PCDAI)	X	X	X	X	X	X	X	X	X	X
Colonoscopy (SES-CD)	X									X
Dose of azathioprine administered	X	X	X	X	X	X	X	X	X	X
Other therapies for CD	X	X	X	X	X	X	X	X	X	X
Concomitant therapies	X	X	X	X	X	X	X	X	X	X
Routine laboratory parameters 	X	X	X	X	X	X	X	X	X	X
Stool sampling 	X	X	X	X	X	X	X	X	X	X

 Hemoglobin, leukocytes, neutrophils, eosinophiles, basophiles, monocytes, lymphocytes, erythrocyte sedimentation rate, CRP, ferritin, iron and transferrin.

 The stool samples will be collected in the morning first stools by the patient at home.

 If patient discontinues the observation period prior to week 96, the date of study discontinuation, the date of last intake of azathioprine and dose, and the reason for discontinuation should be recorded in the electronic CRF

W = week. PCDAI = Pediatric Crohn's Disease Activity Index. SES-CD = Simple endoscopic score for Crohn's disease.

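### Calprotectin remission reached after adding another Crohn's therapy counts as azathioprine maintaining remission, and no calprotectin is scheduled after azathioprine stops, so the week-48 and week-96 proportions risk upward bias

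*Protocol*

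**What the plan says.** Section 6.3 names several reasons for which observation may end before week 96. The first is "Patient discontinues the exposure of interest (azathioprine). The introduction of new treatments to CD during the follow up period"; the sentence continues that such additions do not end participation provided azathioprine is still being taken. Section 6.2 excludes at entry "Patients on methotrexate or under biologics".

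Section 9.1 defines the third primary endpoint as "Proportion of patients who maintain fecal calprotectin remission (< 200 ug/g) at each data collection time point up to week 96"; the week-48 and week-96 endpoint has the same form. Neither states a denominator, a rule for patients who have stopped azathioprine, or a condition on added therapy. Section 9.3 ties clinical remission to being on azathioprine but has no entry for calprotectin remission. Section 10.1 reports the remission proportions for an overall population that it does not define further.

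The chronogram ends in a column headed "W96 or discont", with a stool sample and colonoscopy, and schedules nothing after it. Section 7.2 says calprotectin is not part of routine practice and is not held in the registry. Section 7.1 has Crohn's therapies recorded whenever they change, and section 6.3 has the date of last azathioprine intake recorded at early exit. Persistence on azathioprine is a separate secondary endpoint, given "at each data collection time point up to week 96".

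**The concern.** The stated aim (section 2.4) is the value of azathioprine in maintaining calprotectin remission. Two features of the text pull the late proportions away from it.

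- **Added therapy.** A patient who adds a biologic and keeps azathioprine stays in and scores as maintained once calprotectin is below 200 ug/g. The protocol's own background says that calprotectin falls significantly on infliximab (section 2.2) and that an immunomodulator combined with a biologic may be the most efficacious option (section 2.1).
- **Stopping.** A patient who stops azathioprine may leave observation, and no later calprotectin is then scheduled. If the proportions are taken over patients with a value at the visit, those who did badly on azathioprine tend to be missing from them.

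Both would tend to raise the week-48 and week-96 results. Week 12 is less exposed, because there has been less time to stop or to add therapy.

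**Working it through.** **The plan's own figure.** Section 10.2 states "It is expected to analyze a total of 80 new patients". For a coefficient of 0.75 or more, it claims that "there is a power probability greater than 95% that the lower limit of a one-sided 95% confidence interval is higher than 0.50". Taking 0.75 as the true correlation and using Fisher's z:

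- power = Φ((atanh 0.75 − atanh 0.50)·√(n − 3) − 1.645)
- at n = 80: Φ(0.4236 × 8.775 − 1.645) = Φ(2.073) = 98.1%

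The stated figure of more than 95% is right. It makes no allowance for early exit. About 64 evaluable pairs are needed to stay above 95% (95.2% at 64, 92.5% at 56, 88.4% at 48). It concerns the correlations and says nothing about the primary proportions, for which the plan gives no figure.

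**Illustration of the denominator effect.** Inputs: N = 80 (section 10.2). Assumptions, because the protocol gives neither: a share d stops azathioprine, and q = 75% of stayers have calprotectin below 200 ug/g. The observed-case rate is q. The all-enrolled rate with stoppers as failures is q(1 − d). The gap is q·d.

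| Share stopping | Stayers | Below 200 ug/g | Observed-case | Over all 80 | Gap (points) |
|---|---|---|---|---|---|
| 10% | 72 | 54 | 75% | 67.5% | 7.5 |
| 20% | 64 | 48 | 75% | 60.0% | 15 |
| 30% | 56 | 42 | 75% | 52.5% | 22.5 |
| 40% | 48 | 36 | 75% | 45.0% | 30 |

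At 20% stopping the exact 95% intervals are 63-85% for 48/64 and 48-71% for 48/80. If stoppers are already counted as failures, this gap is zero.

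**Illustration of the added-therapy effect.** This remains whichever denominator is used. At 20% stopping, suppose about 20% or 40% of the 48 remitters (10 or 19 patients) are on an added therapy and are not credited to azathioprine:

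- (48 − 10)/80 = 47.5%
- (48 − 19)/80 = 36.2%

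against 60% when they are credited.

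**Comparison with follow-up regardless of treatment.** If a share h of the 16 stoppers would be below 200 ug/g at the time point, the full-follow-up rate is (48 + 16h)/80: 60% at h = 0, 70% at h = 0.5, 75% at h = 0.75 and 78% at h = 0.9. Against that target the 75% observed-case rate is too high when stoppers do worse than stayers, unbiased when they do equally well, and too low when they do better.

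**The case against.** The strongest reply is that the protocol does not commit to the biased analysis. The wording on ending observation is permissive, no observed-case denominator is fixed, and section 10.1 speaks of the overall population. Denominators are often left to a statistical analysis plan, which could count stoppers as failures from data already collected. Keeping patients who add therapy is an explicit choice in a real-world observational study, and excluding biologics at entry does not contradict their later use.

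Much of this stands, and it rules out several stronger readings that a reader might infer:

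- **That the bias is certain.** It depends on the denominator and on why patients stop. Section 2.1 names intolerance as a reason, and intolerance need not track calprotectin.
- **That the 40-60% relapse rate in section 2.1 gives the stopping share.** Relapse is not discontinuation: under section 6.3 a relapsing patient who adds therapy and keeps azathioprine stays in.
- **That persistence is 100% by construction.** This would need a denominator of patients still observed, which section 9.2 does not state. Last-intake dates are recorded, so persistence over all enrolled can be computed.
- **That the last chronogram column relabels exit values as week 96.** It is an ordinary exit visit, with the discontinuation date recorded and no analysis rule attached.

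Two things are not answered. The section 9.1 endpoint, as worded, credits remission reached after adding another therapy. And no later analysis plan can recover post-stop calprotectin that was never sampled.

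**Conclusion.** The point holds as a likely risk of upward bias in the week-48 and week-96 primary proportions, weaker at week 12. The asymmetry in section 6.3 and the bare threshold in section 9.1 are in the text; the size of the effect is not. The 7.5-30 point range rests on an assumed 75% remission among stayers and 10-40% stopping. It compares two definitions of the endpoint and does not measure error against a known true value. The selection part disappears if stoppers are counted as failures; the added-therapy part does not. The direction is likely where patients stop or add therapy for lack of effect, and is not established for stops due to intolerance.

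**What to change.** In sections 9.1 and 10.1:

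- Use all enrolled patients as the denominator for the maintenance proportions.
- Count azathioprine discontinuation, or start of a new Crohn's therapy, before the time point as not maintained on azathioprine.
- Report as sensitivity analyses the proportion below 200 ug/g regardless of added therapy, and the proportion among those still on azathioprine.
- Compute persistence over all enrolled patients.
- Analyse exit assessments at the week they were made.

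This needs only stop dates and therapy records that sections 6.3 and 7.1 and the chronogram already collect, and changes nobody's treatment. The main cost is a less favourable stated remission rate.

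Optionally, amend section 6.3 so that scheduled stool sampling continues to week 96 after azathioprine stops. The main analysis above does not need it, but an analysis regardless of treatment does. The cost is extra home samples and central-laboratory tests, because calprotectin is not routine care.

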## 7 INFORMATION TO BE COLLECTED

### 7.1 VARIABLES CAPTURED BY THE GEDII REGISTRY

The GEDII Registry allows the collection of socio-demographic, clinical characteristics and outcomes of patients diagnosed with Crohn's disease.

The following variables will be obtained from the Registry:

#### Basal characteristics

- Date of birth
- Sex
- Height
- Weight
- BMI
- Smoking status
- Diagnosis of CD and date

- Date of start of symptoms
- Familial history of IBDs
- Disease presentation (abdominal, constitutional, abdominal + constitutional, anal disease, acute abdomen, fever, anemia, extra-intestinal manifestation, abdominal mass, similar presentation to UC, growth failure)
- Clinical course
- PDAI includes (CD activity): Subjective reporting of the degree of abdominal pain; Presence of extraintestinal manifestations, such as fever, arthritis, rash, and uveitis; Physical examination findings; Weight and height; Hematocrit, erythrocyte sedimentation rate, and serum albumin.  
The scale can be assessed at: [http://www.gedii.pt/\\_scores\\_online](http://www.gedii.pt/_scores_online)
- Routine laboratory parameters (hemoglobin, leukocytes, neutrophils, eosinophiles, basophiles, monocytes, lymphocytes, erythrocyte sedimentation rate, CRP, ferritin, iron and transferrin)
- First episode - Paris classification for CD: age at diagnosis, location, behavior, growth.  
The scale can be assessed at: [http://www.gedii.pt/\\_scores\\_online](http://www.gedii.pt/_scores_online)
- Anal lesion (strictures, abscesses, or fistulas)
- Extra-abdominal manifestations
- Colonoscopy - Simple endoscopic score for Crohn's disease (SES-CD)  
The scale can be assessed at: [http://www.gedii.pt/\\_scores\\_online](http://www.gedii.pt/_scores_online)
- Dose of azathioprine, date of start (Day 1)
- Concomitant therapies (from Day 1)
- Stool sampling - assessment of fecal calprotectin levels:
  - The stools will be sent to a central lab (Departamento de Farmacologia Faculdade Medicina do Porto)
  - Calprotectin testing – sample sent to central laboratory

**Information to be collected at each data collection time points of follow up (every 12 weeks up to week 96) – see Chronogram.**

- Weight/ Height/BMI
- Dose of azathioprine, if changed since previous data collection time point.
- Concomitant therapies (including CD therapies), if changed since previous data collection time point.
- Clinical activity ( PDAI)
- Routine laboratory parameters (hemoglobin, leukocytes, neutrophils, eosinophiles, basophiles, monocytes, lymphocytes, erythrocyte sedimentation rate, CRP, ferritin, iron and transferrin)
- Stool sampling - assessment of fecal calprotectin levels:
  - Calprotectin testing – performed by the Central Laboratory from the samples collected by the patient at home.
- Status: ongoing/discontinuation. If discontinued, reason.

**At week 96:**

- Colonoscopy - Simple endoscopic score for Crohn's disease (SES-CD).

## 7.2 ASSESSMENT OF BIOLOGICAL MARKER - FECAL CALPROTECTIN

Faecal calprotectin is not routinely assessed in the medical practice and therefore is not collected in the GEDII Registry.

[figure not shown]
In this study, faecal calprotectin will be analyzed at Central Laboratory - Departamento de Farmacologia Faculdade Medicina do Porto.

### Collection of stool sample

The stool samples will be collected by the patient according to scheduled time points.

Stool samples will be collected in the morning first stools, using the sample collector device.

**Sample collector device:** stool samples are collected using the sample collector device and send to the laboratory at room temperature. Detailed description can be found in Figure 1. Calprotectin in stools is stable for 7 days at room temperature.

**Figure 1 - Collection of stool sample (sample collector device)**

### Method of calprotectin assessment

### Laboratory testing:

The sample (Sample collector device) will be prepared by the patient at home in the morning before attending to the scheduled appointment. The sample will be returned to the study team who will be responsible for sending the sample for laboratory analysis (Departamento de Farmacologia Faculdade Medicina do Porto).

## 8 EXPOSURE OF INTEREST

Azathioprine is the exposure of interest. This medication may be tailored or optimized according to the physician's clinical criteria **and** taking in to account the label of the product.

## 9 ENDPOINTS

### 9.1 PRIMARY ENDPOINT

- Proportion of patients who achieve fecal calprotectin remission (< 200 ug/g) at week 12.
- Proportion of patients who maintain fecal calprotectin remission (< 200 ug/g) at week 48 and 96.
- Proportion of patients who maintain fecal calprotectin remission (< 200 ug/g) at each data collection time point up to week 96.

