APPENDIX - Chronogram

## 1. Sinopse

Title:	Impact of AZathioprine in maintaining clinical, BIOmarkers and endoscopic remission among new pediatric patients with Crohn's disease treated with exclusive polymeric diet for induction of remission: a 2-year longitudinal analysis from the GEDII Registry – P-BIOAZA
	P-BIOAZA
Scientific Coordinator:	[name]
Disease/Condition	Crohn's disease
Rational	
Thus far, there is limited data on the impact of azathioprine in maintaining fecal calprotectin remission in CD patients.
 
Taking advantage of the valuable tool such as the GEDII Registry, the GEDII promoted a research to investigate the clinical, biomarker and endoscopic outcomes among patients with Crohn's disease and managed with azathioprine in the real-world practice. This study will follow a cohort of pediatric patients with Crohn's disease registered in the GEDII Registry who have induced remission with exclusive polymeric diet and who did initiate azathioprine at diagnosis based on physician's criteria. The cohort will be followed for a period of 2 years.
 
The primary aim of this study is to explore the potential value of azathioprine in maintaining fecal calprotectin remission in pediatric patients with CD.

Research hypothesis:	We hypothesize that pediatric Crohn's disease patients treated with exclusive polymeric diet and with azathioprine at the diagnosis will achieve and maintain fecal calprotectin remission.
Primary Objectives:	
Among patients with Crohn's disease at study inclusion, registered in the GEDII Registry:
 
 
•To evaluate the impact of azathioprine in inducing calprotectin remission (calprotectin levels < 200 ug/g) at week 12.
 
•To evaluate the impact of azathioprine in maintaining calprotectin remission (calprotectin levels < 200 ug/g) at week 48 and 96
 
•To evaluate the impact of azathioprine in maintaining calprotectin remission throughout a follow up period of 96 weeks.
 

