Secondary Objective(s):	
 
•To explore the association of the fecal calprotectin assessment regarding clinical and endoscopic outcomes.
 
•To explore the association of fecal calprotectin levels with clinical outcome throughout a follow up period of 96 weeks.
 
•To explore the association of fecal calprotectin levels with endoscopic activity throughout a follow up period of 96 weeks.
 
•To evaluate the impact of azathioprine in inducing clinical remission at week 12.
 
•Among patients who achieve clinical remission with azathioprine, to evaluate the maintenance of clinical remission up to week 96.
 
•To evaluate the impact of azathioprine in inducing endoscopic remission at week 96.
 
•To evaluate the impact of azathioprine in maintaining endoscopic remission throughout a follow up period of 96 weeks.
 
•To evaluate the rate of azathioprine persistence throughout a follow up period of 96 weeks
 

	
 
•To evaluate the time until loss clinical remission
 

Study Design:	
Multicenter, prospective, observational study designed to gather and analyze data on a consecutive cohort of subjects with CD who initiated therapy with azathioprine, according to physician's clinical decision. There is no imposed experimental intervention and prescribing decisions from the study physicians will be independent of patient's participation in this study.
 
The maximum overall duration of observation for each patient is 96 weeks since the start of observation period (Day 1).

Inclusion Criteria:	
Study patients must fulfill the following criteria:
 
 
1. Male or female patients, <18 years;
 
2. Patients who are registered in the GEDII Registry;
 
3. Patients who have been treated with exclusive polymeric diet and start azathioprine at diagnosis
 
 
AND who meet one of the following:
 
 
o Moderate/Severe disease (PCDAI>31) at start of study with fecal calprotectin levels > 100 ug/g
 
o Mild disease (PCDAI>11<30) with fecal calprotectin levels > 100 ug/g and/or Endoscopic activity (Simple endoscopic score for Crohn's disease [SES-CD] ≥ 3)
 
 
 
4. Patients who gave their informed consent.
 

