## 6 STUDY POPULATION

### 6.1 INCLUSION CRITERIA

Study patients must fulfill the following criteria:

1. Male or female patients, <18 years old
2. Patients who are registered in the GEDII Registry;
3. Patients who induce remission with polymeric diet and start azathioprine at diagnosis

**AND** who meet one of the following:

- o Moderate/Severe disease (PCDAI>30) at start of study
- o Mild disease (PCDAI<30) with fecal calprotectin levels > 100 ug/g and/or Endoscopic activity (Simple endoscopic score for Crohn's disease [SES-CD] ≥ 3

4. Patients who gave their informed consent.

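### The week-12 calprotectin endpoint counts patients who were already below 200 ug/g on Day 1, and are still below it, as having achieved remission

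*Protocol*

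**What the plan says.** The synopsis sets the first primary objective as "To evaluate the impact of azathioprine in inducing calprotectin remission" (below 200 ug/g) at week 12, and section 3.1 repeats it. The endpoint in section 9.1 is "Proportion of patients who achieve fecal calprotectin remission (< 200 ug/g) at week 12". The next endpoint in the same list is "Proportion of patients who maintain fecal calprotectin remission (< 200 ug/g) at week 48 and 96", so the protocol itself separates achieving remission from maintaining it.

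The calprotectin conditions at entry are:

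- Section 6.1, moderate/severe: "Moderate/Severe disease (PCDAI>30) at start of study", with no calprotectin value.
- Synopsis, moderate/severe: a PCDAI condition "at start of study with fecal calprotectin levels > 100 ug/g".
- Section 6.1, mild: "Mild disease (PCDAI<30) with fecal calprotectin levels > 100 ug/g and/or Endoscopic activity" (SES-CD of 3 or more). The synopsis has the same and/or.

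Section 10.1 summarises the remission proportions for the overall population and for subsets by disease activity at inclusion. It does not split them by Day-1 calprotectin. The Appendix chronogram schedules a stool sample and a colonoscopy on Day 1.

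For endoscopy, section 9.2 counts patients who achieve remission ("SES-CD ≤ 2) at week 96"). The synopsis words the week-96 objective as inducing endoscopic remission; section 3.2 words it as maintaining it.

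**The concern.** Achieving or inducing a state implies a change from not being in it. The proportion measures that change only if the denominator is limited to patients who are outside the state at the start. Here the only calprotectin threshold used at entry (100 ug/g) lies below the remission threshold (200 ug/g), and some routes set no calprotectin threshold at all. The week-12 figure can therefore mix two groups: patients who moved from 200 or above to below 200, and patients who began below 200 and stayed there.

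This is a single cohort. There is no comparator in which the same mix would appear and cancel, and the planned 95% confidence interval reflects sampling error only. A reader of the result could not tell how much of the proportion is induction and how much is entry mix.

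**Working it through.** **The plan's own figure.** The only sample-size statement (section 10.2) concerns a correlation: N = 80, r = 0.75, one-sided 95% lower limit above 0.50, power above 95%. By Fisher's z, power = Φ[(atanh 0.75 − atanh 0.50) × √(80 − 3) − 1.645] = Φ(0.4236 × 8.775 − 1.645) = Φ(2.07) = 98.1%. The statement reproduces, but it says nothing about the week-12 proportion.

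**Do the entry and endpoint definitions overlap?**

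| Entry route | Calprotectin needed | Can Day-1 value be below 200? |
|---|---|---|
| Moderate/severe, section 6.1 | none | yes, any value |
| Moderate/severe, synopsis | above 100 | yes, between 100 and 200 |
| Mild, via calprotectin (both places) | above 100 | yes, between 100 and 200 |
| Mild, via SES-CD of 3 or more (both places) | none | yes, any value |

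Every route admits patients who already satisfy the remission definition, whichever version of the criteria applies.

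**How large could the effect be?** Let f be the share with Day-1 calprotectin below 200, s the share of those still below 200 at week 12, and p the true conversion rate among patients starting at 200 or above. Then

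- reported proportion = f·s + (1 − f)·p
- excess over p = f·(s − p)

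The protocol gives none of f, s or p; all three are assumed. With s = 0.85:

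| f | p = 0.40: reported (excess) | p = 0.50: reported (excess) |
|---|---|---|
| 2% | 40.9% (0.9 points) | 50.7% (0.7 points) |
| 5% | 42.25% (2.25 points) | 51.75% (1.75 points) |
| 10% | 44.5% (4.5 points) | 53.5% (3.5 points) |
| 20% | 49.0% (9.0 points) | 57.0% (7.0 points) |

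For example, with f = 10% and p = 0.40: 0.10 × 0.85 + 0.90 × 0.40 = 0.085 + 0.360 = 0.445.

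The limiting case shows the mechanism. If no patient converts (p = 0) and all who start below 200 stay there (s = 1), the endpoint still reports 10% (8 of 80) for f = 10% and 20% (16 of 80) for f = 20%.

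The excess is positive only while s exceeds p, which is an assumption, and it goes to zero with f.

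**What does restricting the denominator cost?** Wilson 95% intervals at an observed 50%:

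| Patients analysed | 95% interval |
|---|---|
| 80 (all) | 39.3-60.7% |
| 72 (f = 10%) | 38.7-61.3% |
| 64 (f = 20%) | 38.1-61.9% |

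**The case against.** The strongest reply is that the effect may be negligible. The cohort is newly diagnosed, so few patients may have low calprotectin on Day 1. Section 2.2 cites a pooled sensitivity of 0.978 for calprotectin in suspected pediatric disease, which points the same way, although it gives no cut-off and so does not bound the share below 200. The half-width of the 95% interval at 50% with 80 patients is about 11 points, larger than any excess in the table. This stands as a limit on the size. It does not repair the definition, and a wider sampling interval does not remove a shift in what is being estimated.

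A second reply is that the share below 200 at week 12 is a valid description of status, and that denominators are usually left to the SAP. The first part is fair: the fault lies in calling that share achievement or induction. The second part is weaker, because section 10.1 already names the overall population and the subsets.

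Several stronger readings are tempting but not supported:

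- *Everyone who enters below 200 is an automatic success.* Such a patient counts only if still below 200 at week 12.
- *Moderate/severe patients need no calprotectin value.* That is true of section 6.1 but not of the synopsis, which asks for more than 100.
- *The result is known to be inflated by several points.* Every input to that figure is assumed.
- *The endoscopic endpoint has the identical flaw.* Patients can enter with SES-CD of 2 or less, but section 3.2 speaks of maintaining remission at week 96. Restricting to Day-1 SES-CD of 3 or more would remove exactly the patients who could maintain it.
- *The corrected endpoint would isolate an azathioprine effect.* It would not: all patients also receive polymeric diet and there is no comparison group.

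**Conclusion.** The point holds as a mismatch between the wording of the first primary objective and endpoint and the patients who are counted. It follows from the entry criteria and sections 9.1 and 10.1 without any numerical assumption.

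The size cannot be determined from the protocol. Under assumed retention of 85% and true conversion of 40-50%, it runs from 0.7-2.3 points (2-5% starting below 200) to 3.5-9 points (10-20% starting below 200), and could be close to zero. For the endoscopic endpoint, the documents support only the conclusion that the required starting state is unsettled.

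**What to change.** - **Week-12 endpoint.** Define it as the proportion with calprotectin below 200 ug/g at week 12 among patients with Day-1 calprotectin of 200 or more. Report patients with Day-1 values below 200 separately, as the proportion who remained below 200. Amend section 10.1 to match.
- **Week-96 endoscopic endpoint.** First reconcile the synopsis (inducing) with section 3.2 (maintaining). Then report SES-CD of 2 or less by Day-1 status: achieved among those starting at 3 or more, maintained among those starting at 2 or less.
- **Entry criteria.** The calprotectin requirement for moderate/severe disease differs between the synopsis and section 6.1. The two must be reconciled. The endpoint change is needed under either version.

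The cost is small: wording in the protocol and analysis plan, with no new visit, sample or colonoscopy. The downside is a smaller denominator for the week-12 endpoint, which at an observed 50% widens the 95% interval by about 1 to 2.5 points in total for 72 or 64 patients (22.6 or 23.8 points wide, against 21.4 with 80).
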